- f. Research on individual or group behavior or characteristics of individuals such as perception studies, cognition, game theory or test development where the investigator does not manipulate subjects and will not involve significant stress to subjects.
- g. Research conducted in established or commonly accepted educational settings, normal educational practices, e.g. i) research on regular and special education strategies or ii) research on the effectiveness of or the comparison among instructional techniques, curricula or classroom management techniques.
- h. Research involving the use of educational tests (cognitive, diagnostic, aptitude, achievement), survey procedures, interview procedures or observation of public behavior unless: i) information obtained is recorded in such a manner that subjects can be identified, either directly or through identifiers linked to the subject, or ii) any disclosure of subject's responses outside the research could reasonably place the subject at risk of criminal or civil liability or be damaging to the subjects financial standing, employability or reputation.

B. Does this research involve the use of Investigational New Drugs(s)? No Yes
If yes, Drug Name: Company:
IND Number:
Phase: I II III IV

C. Does this research involve the use of an Investigational Medical Device? No
 Yes

If yes,

Device Name:
Company:
IDE Number:

D. Human subjects from the following population will be involved in this study (Check all that apply):

Minors (under the age of 18 years)
 Individuals with mental illness
 Individuals with intellectual disability

Pregnant Women
 Prisoners
 The Unborn

E. Will a student conduct the research?

Yes

No

If yes, What is student's previous experience?

What is the additional training provided by the faculty mentor, if needed?

Will the student be supervised during invasive procedures?

No

Yes

If no, please provide a detailed explanation as to why.

II. Abstract - Brief (200 words or less) description of purpose, methods, and expectation.

The high prevalence of myopia – especially in Asian countries – is well documented, as are the sight-threatening complications of high or degenerative myopia. Retinal detachment, glaucoma, vitreal degeneration and focal retinal changes may occur secondary to the progressive axial elongation of the eye with age. Specialty rigid lenses have long been shown to lessen this progression in the pediatric population; orthokeratology (ortho-k) lenses are worn at night and change the corneal topography to correct low to moderate amounts of myopia. Most of the studies on orthokeratology were conducted on Asian children. To the best of our knowledge, no study has been done on African American (AA) children. Our project seeks to investigate the efficacy of ortho-k in slowing axial elongation and myopic progression in AA children compared to that in other races.

III. Introduction/literature review: Please describe the research rationale, aim, and hypothesis with relevant background (citing published studies). Also, provide a list of pertinent references.

Orthokeratology (ortho-k), when used for partial or full correction of myopia, has been shown to slow myopic progression in children by 36-56% as compared to their spectacle or contact-lens wearing peers.¹ This effect is achieved by limiting the axial elongation of the eye,^{1,2,3,4} which is of particular concern in high myopes (>6.00D) and children, where myopic progression has been shown to proceed at a faster rate than average.¹ As early intervention is considered beneficial if not essential, Ortho-k as a treatment modality for diminishing myopic progression has, to our knowledge, been studied mostly in Asian children.

The safety and efficacy of ortho-k as a means of decreasing myopic progression was well established by the Children's Overnight Orthokeratology Investigation (COOKI), who evaluated refractive error, visual changes and ocular health over a period of 6 months in myopic children.⁷ The Longitudinal Orthokeratology Research in Children (LORIC) study looked at axial elongation in children as old as 12 years, and found that ortho-k decreased axial elongation by approximately 50% compared to be-spectacled controls.² They also noted, however, high variability amongst the children that limits the clinician's ability to predict the outcome of the intervention.² The Corneal Reshaping and Yearly Observation of Myopia (CRAYON) study confirmed that patients fit with ortho-k lenses showed less change in axial length and vitreous chamber depth when compared to subjects wearing soft contact lenses.³ Other more recent studies by Santodomingo-Rubido et al,⁷ Kakita et al⁴ and Charm et al¹ confirm this decrease in axial elongation using IOL Master measurements.

The most commonly accepted theory on how orthokeratology decreases axial elongation relies on the peripheral defocus created on the retina by the corneal changes made by the rigid lens.⁹ Hoogerheide et

al showed that those at greatest risk for myopic progression were those whose peripheral refraction was hypermetropic¹⁰ – that is, they had a hyperopic peripheral ‘defocus’. A number of studies have since suggested that treatment approaches to myopia correction should address this peripheral refraction as a means of slowing further axial elongation.⁹ When looking at subjects treated with ortho k, we see that the lenses do in fact introduce a peripheral myopic defocus while leaving the central refraction more or less emmetropic.⁹ With this study, we hope to expand potential application of orthokeratology to a novel population, AA children.

References

Eligible participants will be informed of the benefits and risks of the study both verbally and in writing. Ethics approval will be obtained from the Institutional Review Board at the Illinois College of Optometry. Inclusion criteria include: the subjects, aged from 6 to 13 years, must have yearly myopia progression ≤ -1.00 D , with a myopic prescription between -1.00D and -6.00D in at least one eye with refractive astigmatism <1.50 D. Visual acuity must be at least logMAR 0.10 (Snellen 20/25) or better at baseline examination in both eyes through best corrected manifest refraction. Ocular examination must not reveal any strabismus,

ocular pathology or contraindications for orthokeratology lens wear, and no ocular trauma history. Subjects must be in good general health with no systemic conditions that might impact their ocular health or refractive error. They must be willing to sleep a minimum of six hours per night. Finally, subjects must be willing and able to present to clinic for all necessary follow-up care. Subjects will be excluded if their prescription falls outside the refractive guidelines, have a history of any type of trauma or ocular surgery, have a history of prior experience with myopia control treatment, are amblyopic or if they are current gas permeable lens wearers. They will be discontinued from the study if they are non-compliant with the treatment protocol or do not achieve a desirable subjective result.

Baseline examination will include measurement of logMAR acuity (monocular and binocular), subjective manifest refraction and auto-refraction (with cycloplegia) with measurement of peripheral refraction, anterior segment evaluation, corneal topography (tangential map recordings, including pupil measurement), IOL Master measurement of axial length and ultrasound pachymetry. Refractions will be performed with a maximum-plus endpoint which gives maximum vision. Objective measurements (including IOL Master, autorefractor and pachymetry) will be taken in triplicate and averaged at both baseline examination and 6-month examination. Cycloplegic measurements will be taken at the baseline, 6-month evaluations, 12-month evaluations, and 24-month evaluations. Measurements will be taken approximately 30 minutes after instillation of drops, in this order; Proparacaine 0.5%, Tropicamide 1%, and Cyclopentolate 1%.

After baseline examination, specialty orthokeratology (Euclid) lenses will be ordered for those assigned to the treatment arm based on topography, non-cycloplegic refraction, pupil size, and horizontal visible iris diameter. Subjects will have a dispensing appointment as well as after-care appointments at 1-day (+/- 1 day), 1-week (+/-3 days), 1-month (+/-1 week), 6-month (+/-15 days), 12-month (+/-15 days), 18-month (+/-15 days), and 24-month (+/-15 days). Lenses and solutions will be provided at no cost to the subject by examiners.

The subjects wearing spectacles will have a baseline examination, and follow up appointment at 6-month, 12-month, 18-month, and 24-month. New spectacle lenses will be provided at no cost to the subject if their current lenses differ from their spectacle prescription (as determined by the examiner) by more than 0.50D in either sphere or cylinder power. Throughout the study, spectacles will also be updated at no cost for every 0.50D change in either the sphere or cylinder measurement. If spectacles are lost or broken, the investigators will cover 50% of the cost of replacement. The same protocol applies for those subjects wearing soft contact lenses.

The principal investigator, co-investigator and supervisor, who will act as unmasked examiners, will collect all examination data except axial length. Masked observers (up to a maximum of 3) will be trained by the principal investigator in the use of the IOL Master and will perform all measurements with the instrument. Objective measurements will be repeated three times and averaged to minimize inter-operator differences. Refractions will be performed at each examination and will follow a specific protocol to generate a balanced, maximum-plus endpoint. All subjects will be required to wear the prescribed treatment every day for the 6-month period under investigation.

Repeated measure ANOVA will be performed to determine if change of refractive error and axial length is different comparing subjects in the ortho-K group vs. ones in the control groups.

V. Describe the potential scientific benefit(s) of the study.

Those with myopia would most immediately benefit from this research. Subjects who were not treated with ortho-k at a young age would benefit from evidence that the lenses are effective in an older population. Another beneficiary would be the segment of the population at highest risk for degenerative changes: those who have high (>6.00 diopters (D)) myopic refractive errors or those whose axial length elongates at a faster rate than average. These subjects would be most poised to benefit from this research, as axial length has been directly linked to increased risk of ocular pathology.

VI. Outline the risks to the subjects and precautions that will be taken to minimize them. Note: risks may extend beyond physical risk and may include psychological, social, and/or financial risk(s)

While orthokeratology is considered to be a safe and effective procedure by the American Academy of Ophthalmology, potential risks include: mild lens binding upon awakening, corneal staining, solution allergy, fluctuating vision, irritation, redness, and in rare cases, corneal infection. To minimize risks, patients will be well educated on proper lens wear and care and will be provided with the appropriate solutions at no cost. Patients will also be given written instructions. Patients will also be seen for frequent follow-up care and will have the 24 hour emergency contact information for the Urgent Care Service at the Illinois Eye Institute.

VII. Describe the methods to be used to insure confidentiality of data.

In order to ensure confidentiality, each subject will be randomly assigned a unique study number. Therefore, all data will be tracked by number rather than by an IEI chart number, name, or initials. Only the researchers will have access to that information. All data throughout the study will be coded using this ID number. The randomized numbers will be kept separate from the data collected.

VIII. All research requires that the subject be aware of the fact that they are participating in a research project. This is accomplished using an Informed Consent Process that includes a verbal and written description of the project and other relevant information. The Consent Form is used for adults (individuals over the age of 18) and children or individuals who are not their own legal guardian (to obtain assent). The form must be written at an eighth grade (or lower) level and fully explained to the research subject. It must also be signed by the research subject, a legal guardian, if necessary, and a witness. Please refer to Handbook For Investigator for specific guidelines to be followed.

A. Consent forms should be attached.

B. Describe the process that will be used to obtain consent, including information on who will obtain the consent, and where and when will it be obtained.

Investigators will consent the parents and children in either pediatric clinic or contact lens clinic.

IX. Please provide additional information that will be beneficial to the IRB.

The following apply to proposals that are being submitted for review by the Research Resource Committee only:

Pilot Study

Certain studies are meant to obtain preliminary information in order to determine if a larger more involved study would be worthwhile. Such studies are considered pilot studies. Sometimes these studies require a minimum budget other times the budget may be quite extensive. The research allocation committee may look at your request in a different manner if your request for funding involves a pilot study. Many of the projects funded are considered to be pilot studies.

X. Budget

In writing research budgets for ICO funding the following factors should be considered.

1. The total faculty research budget is limited. The amount can vary with the academic year. Funding for large projects (generally over \$5000) is usually not a possibility. The Research Resource Committee will do its best to support faculty requests on a first come first supported basis. The fiscal year ends on June 30th. Requests for funds should be submitted as early as possible during the academic year. Include all itemized costs for funding. Approved funds not spent by July 1st (end of the academic year) are deposited back to the general fund. A new request will need to be submitted.

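### Averaging three readings by one observer does not remove that observer's offset, and the plan is inconsistent on whether objective readings after 6 months are triplicates

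*Combined protocol and SAP*

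**What the plan says.** All of this is in Section IV (Summary of methods) of the combined protocol and SAP.

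- **Who measures.** "Masked observers (up to a maximum of 3) will be trained by the principal investigator in the use of the IOL Master", and they "will perform all measurements with the instrument". The principal investigator, co-investigator and supervisor are unmasked and "will collect all examination data except axial length". Autorefraction and pachymetry therefore also fall to up to three people.
- **Stated purpose of the repeats**, in the same paragraph: "Objective measurements will be repeated three times and averaged to minimize inter-operator differences". No visit is named.
- **Timing of the repeats**, in the earlier paragraph on the baseline examination: "Objective measurements (including IOL Master, autorefractor and pachymetry) will be taken in triplicate and averaged at both baseline examination and 6-month examination".
- **Visits.** The trial runs for 24 months. After baseline, control children have "follow up appointment at 6-month, 12-month, 18-month, and 24-month"; the ortho-k arm has the same four visits plus early after-care.
- **Analysis.** "Repeated measure ANOVA will be performed to determine if change of refractive error and axial length is different" between the groups. No observer term is mentioned.

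The plan does not say whether one observer takes all three readings at a visit. It has no rule on which observer sees a child at successive visits, no agreement check between observers, and no instruction to record who took a reading.

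**The concern.** The plan offers averaging as its protection against differences between operators. Three readings by one person share that person's systematic offset, so their mean carries it in full. If someone else measures the child at a later visit, the difference between the two offsets enters the change score, however many repeats were taken. If observer identity is not recorded, this may be impossible to examine afterwards.

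The two statements on triplicates also give different instructions for the visits after 6 months. A team that follows the narrower one may compare an averaged baseline with a single reading at 24 months. Axial length and refractive error are the two outcomes named for the ANOVA, and only 40 to 60 children are to be recruited, so avoidable measurement error is worth removing.

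**Working it through.** **Inputs.** From the plan: three readings averaged, one to three IOL Master observers, a baseline and four common follow-up visits, and 40 to 60 children (20 to 30 per arm if allocation is 1:1, which the plan does not state). The plan gives no operator SD, repeatability, effect size, alpha or power, so there is no figure to reproduce. All SDs below are assumptions.

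**Model.** Reading = true value + operator offset (SD so) + repeat error (SD sr). With m readings by one operator at each of two visits, the measurement-error variance of a change score is:

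- same operator at both visits: 2·sr²/m
- different operators: 2·so² + 2·sr²/m

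The number of readings m divides only the repeat term.

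**Step 1: what averaging achieves for axial length.** Take sr = 0.02 mm and m = 3. With the same operator, √(2 × 0.02²/3) = 0.016 mm. With different operators:

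| Assumed so (mm) | Error SD, operators differ (mm) | Error SD, 3 operators at random (mm) |
|---|---|---|
| 0.01 | 0.022 | 0.020 |
| 0.02 | 0.033 | 0.028 |
| 0.05 | 0.073 | 0.060 |
| 0.10 | 0.142 | 0.117 |

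For example, √(2 × 0.02² + 2 × 0.02²/3) = 0.033. The random column multiplies 2·so² by 2/3. With so = 0.05 mm and different operators, going from one reading to three lowers the error SD only from 0.076 to 0.073 mm; the floor, √2 × 0.05, is 0.071 mm. Simulation for so = 0.02 and 0.05 mm agreed with these formulas.

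**Step 2: how often the operator changes.** With K operators assigned at random, a baseline-to-visit pair shares an operator with probability 1/K: 1 for one operator, 1/2 for two, 1/3 for three. Shared pairs carry no offset. With three operators, (1/3)⁴ = 1.2% of children would keep one operator through all five visits by chance.

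**Step 3: consequence for axial length.** Assume a true-change SD of 0.2 to 0.3 mm. With so = 0.02 mm, a switch raises the total SD by 1.0% (√[(0.04 + 0.001067)/(0.04 + 0.000267)] = 1.010) to 0.4% (the same with 0.09 in place of 0.04). Assume also a group difference of 0.20 to 0.25 mm, a two-sided 5% test, 20 or 30 per arm and three operators at random. The power loss is then at most 0.4 points at so = 0.02 mm, 0.2 to 2.6 points at 0.05 mm, and about 1 to 10 points at 0.10 mm.

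**Step 4: triplicate at baseline, single reading later.** With the operator held constant, the error variance of change is sr²/3 + sr²/3 = 2·sr²/3 for two triplicates, and sr²/3 + sr² = 4·sr²/3 for a triplicate and a single reading. The error variance doubles whatever sr is, so the error SD rises by a factor of √2.

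- Autorefraction, sr = 0.25 D: 0.25 × √(2/3) = 0.20 D against 0.25 × √(4/3) = 0.29 D. Half that SD gives 0.10 against 0.14 D; twice gives 0.41 against 0.58 D.
- Axial length, sr = 0.02 mm: 0.016 against 0.023 mm.

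**The case against.** A reader might infer more than the documents support, and the other side is right on several counts.

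- **That the offset sits in every change score.** It does not. A constant offset cancels when the same observer measures both visits, and a maximum of three observers allows for just one.
- **That averaging can never reduce operator differences.** This assumes one observer takes all three readings. That is the natural reading, but the plan does not say so; readings split between observers would reduce the offset.
- **That the treatment comparison is biased.** Axial-length observers are masked and children are randomised. A steady imbalance of observers between arms cancels if each child keeps the same observer. Changes over calendar time affect both arms alike when they are enrolled concurrently. Bias needs switching that differs by arm, and the documents give no mechanism for that.
- **That later readings are single.** The baseline-examination paragraph does not say so, and the later paragraph, having no limit, points the other way.
- **That nothing else controls operator differences.** All IOL Master observers are trained by the principal investigator, which is a real control.

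The axial-length effect is also slight on plausible assumptions, as Step 3 shows. These points limit the size of the problem. They do not make averaging by one observer do what the plan says it does, and they do not tell staff how many readings to take at 24 months. Training without an agreement check leaves the remaining offset unknown.

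**Conclusion.** The point holds in a limited form, in two parts. First, on its natural reading the stated safeguard reduces repeat error only, and operator offset remains wherever the observer differs between visits. For axial length this is mainly noise and probably small, unless the operator SD is well above 0.02 mm, which the documents cannot settle. Second, the two statements on triplicates conflict for the 12-, 18- and 24-month visits. If the narrower one is followed with single later readings, the measurement-error variance of change from baseline doubles. That ratio needs no assumed SD; the 0.29 against 0.20 D for autorefraction rests on the assumed 0.25 D. Its effect on the refractive outcome depends on whether autorefraction supplies that outcome, which the plan does not say, and on the between-child spread, which it does not give.

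The case for acting rests on an incorrect rationale, a conflict in the text and a nearly free remedy, not on a large operator effect.

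**What to change.** **Baseline-examination paragraph.** State that objective measurements are taken in triplicate and averaged at baseline and at every follow-up visit where the measurement is made (6, 12, 18 and 24 months), so that it agrees with the later paragraph.

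**Observer paragraph.** Replace the sentence on inter-operator differences with text to this effect:

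- The three readings are averaged to reduce repeat error.
- The same masked observer measures a child's axial length at all visits where possible, and likewise the same examiner for autorefraction and pachymetry.
- When a substitute is needed, the substitute takes all three readings.
- Observer ID is recorded at each visit, and a sensitivity analysis may include observer.

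Sharing the readings among whichever observers are present is a poor fallback. If the child's usual observer is away, at most two others remain. One reading from each gives √(1.5 × 0.02² + 0.02²/3 + 0.02²/2) = 0.031 mm on the same assumptions, little better than the 0.033 mm of a simple switch.

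**Cost.** Booking becomes slightly less flexible, and there are up to two extra short readings per measurement at each later visit. No new staff or equipment is needed.
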